4.5.1.1. Adverse Events of Special Interest

The following AEs of special interest (AESI) will be reported to characterise the important potential risks (safety concerns) for bepirovirsen:

- ALT increase.
- Vascular inflammation and complement activation.
- Thrombocytopenia.
- Renal injury.
- Injection Site Reactions.

In addition, the following AEs which are identified as significant events but not as safety concerns will be reported:

- Immune-mediated events
- Neutropenia

An up-to-date list of standardized MedDRA Queries (SMQ)s, high level terms (HLTs) or individual PTs used to identify AESIs is periodically updated and stored in a central location. At the time of Database Lock (DBL), the latest version of the terms will be extracted and used to identify AESIs.

All AESIs and significant events will be summarized by SOC and PT, and summarized by SOC, PT, and maximum grade. Serious AESIs will be summarized by SOC and PT. All AESIs and significant events will be listed. Also, a listing of non-fatal SAEs will be produced.

Separate outputs will be created for each AESI and significant event category (ALT increase, vascular inflammation and complement activation, thrombocytopenia, renal injury, immune-mediated events, neutropenia, and injection site reactions) to explore the data in more detail if data permits.

Event Characteristics: The characteristics of all event occurrences during the post-baseline period will be summarized, which looks at event characteristics (serious, resulting in hospitalisation, drug-related, leading to withdrawal, maximum intensity, or maximum grade, fatal), number of events per participant, outcome, maximum grade or intensity and action taken. Event characteristics will be described by the proportion based on all subjects and the proportion based on subjects with the event for each of these items.

4.5.2. Additional Safety Assessments

4.5.2.1. Laboratory Data

Only central lab data will be used for summary analyses and figures; local lab data will be included in listings, as appropriate. The clinical laboratory tests are listed in Table 11 of protocol Section 10.2.

4.5.2.2. Laboratory Reporting

The haematology, clinical chemistry, urinalysis, and additional parameters to be tested are listed in the Appendix 2 of the Protocol.

Summary statistics for changes from baseline for each numeric parameter at each time point will be presented, separately for all clinical chemistry (along with liver function parameters) parameters, all haematology parameters, and all urinalysis parameters.

Also, summaries of worst-case grade increase from baseline grade will be provided for all the lab tests that are gradable by DAIDS grading system Version 2.1 [National Institute of Allergy and Infectious Diseases. Division of AIDS, July 2017]. These summaries will display the number and percentage of participants with a maximum post-baseline grade increasing from their baseline grade. For laboratory tests that are graded for both low and high values, summaries will be done separately and labelled by direction.

For lab tests that are not gradable by DAIDS Version 2.1, summaries of worst-case changes from baseline with respect to normal range will be generated. Decreases to low, changes to normal or no changes from baseline, and increases to high will be summarized for the worst-case post-baseline. If a subject has a decrease to low and an increase to high

during the same time interval, then the subject is counted in both the “Decrease to Low” categories and the “Increase to High” categories. Also, laboratory values outside of normal range will be listed.

Shift tables showing baseline toxicity versus maximum post-baseline toxicity for each grade (Grade 1, Grade 2, etc.) for laboratory, chemistry and haematology parameters will be provided.

The worst-case urinalysis results post-baseline relative to baseline will be summarized.

Increase to Grade 3 or higher lab abnormalities for platelets, ALT, AST, , WBC, total bilirubin, serum creatinine, ACR will be summarized.

Scatter plots of maximum ALT vs baseline ALT as well as maximum total bilirubin vs maximum ALT will be presented. Also, plots showing mean actual and change from baseline values of the parameters over time will be presented. Listings of urinalysis data as well as lab data for subjects with values outside the normal range will also be created.

4.5.2.3. Monitoring Event Reporting

Liver monitoring and stopping event reporting will be summarized and listed. The Liver monitoring and stopping criteria are described in the protocol Section 7.1.1.

Haematological monitoring will be summarized and listed based on laboratory parameters (platelet count and anti-platelet antibodies). The haematological monitoring criteria are described in the protocol Section 7.1.2.

Data for potential Drug induced kidney injury (renal) monitoring events will be captured in the eCRF; they will be summarized. The kidney injury monitoring criteria are described in the protocol Section 7.1.3.

Data for potential drug induced vascular injury and complement monitoring will be captured in the eCRF; they will be summarized. The drug induced vascular injury and complement monitoring criteria are described in the protocol Section 7.1.4.

4.5.2.4. Vital Signs

Summary statistics for absolute values and change from baseline (by each time point and treatment group) in temperature, pulse rate, respiratory rate, systolic blood pressure (SBP), diastolic blood pressure (DBP) will be provided.

Also, by-treatment summaries of grade increase in temperature, SBP and DBP will be provided separately. These summaries will display the number and percentage of participants with any grade increase, increase to Grade 2, increase to Grade 3 and increase to Grade 4 (for temperature only), for worst case post-baseline only. The summaries will be produced for worst case post baseline only. The DAIDS grading system Version 2.1 [National Institute of Allergy and Infectious Diseases. Division of AIDS, 2017], will be used for grading: The grade definition for temperature is: Grade 1 (38.0°C – <38.6°C),

Grade 2 ($38.6^{\circ}\text{C} - <39.3^{\circ}\text{C}$), Grade 3 ($39.3^{\circ}\text{C} - <40.0^{\circ}\text{C}$), Grade 4 ($\geq 40.0^{\circ}\text{C}$). The grade definition for SBP is Grade 1 (140-159), Grade 2 (160-179), Grade 3 (≥ 180). The grade definition for DBP is Grade 1 (90-99), Grade 2 (100-109), Grade 3 (≥ 110). DAIDs does not include a Grade 0, please refer to the OPS for instruction on how to present values that don't meet the criteria for Grade 1+. Participants with missing baseline values are assumed to have a normal baseline value.

4.5.2.5. ECG

When data is collected as triplicate, the average of triplicate ECG measures for each patient will be used.

ECG data (absolute values and change from Baseline) will be summarised by each timepoints and randomised groups only for the end of study analysis.

[figure not shown]
CCI

A large black rectangular redaction box covers the majority of the page content below the 'CCI' label.

4.7. Changes to Protocol Defined Analyses

There were no changes or deviations to the originally planned statistical analysis specified in the protocol. (Dated : [26th July 2023]).

CCI

A large black rectangular redaction box covers the majority of the page content below the 'CCI' label.

CCI

CCI

To assess the secondary objectives of estimating the relative bioavailability of Group 2 compared to Groups 3 and 4, approximately CCI subjects will be randomized into Groups 3 and 4 (approximately CCI per arm). This will provide the same number of subjects in the applicable sites of administration (thigh and abdomen) compared to Groups 1 and 2.

6. SUPPORTING DOCUMENTATION

6.1. Appendix 1 Study Population Analyses

Unless otherwise specified, the study population analyses will be based on the Safety Analysis Set. A summary of the number of participants in each of the participant level analysis set will be provided.

Study population analyses including analyses of participant disposition, demographic and baseline characteristics, protocol deviations, and prior and concomitant medications and medical history. Details of the planned displays are presented in the OPS document.

6.1.1. Participant Disposition

A summary of the number and percentage of patients who were screened including screen failures will be provided. Reasons for failure will be included.

A summary of the number and percentage of participants who completed the study, as well as those who prematurely withdrew from the study will be provided. Reasons for study withdrawal will be summarized.

Summaries of disposition, adverse events leading to withdrawal and reasons for withdrawal will be presented, as defined in the OPS.

Listings of reasons for study withdrawal, screen failure will be provided.

6.1.2. Demographic and Baseline Characteristics

Demographic characteristics including sex, age, ethnicity, race, height, and weight will be summarized with descriptive statistics.

Baseline characteristics including but not limited to BMI, hypertension, diabetes, serum creatinine, urine ACR, platelets, ANCA, complement C3, complement C4, C Reactive Protein will be summarized with descriptive statistics. Continuous characteristics will be presented using summary statistics (n, Mean, SD, Median, Min, Max) and may also be categorized and summarised using n (%).

Past medical conditions and current medical conditions as of screening will be summarized as “Summary of Past and Current Medical Conditions”.

Substance use, including smoking history, tobacco use, alcohol and drug history will be summarized.

6.1.3. Protocol Deviations

Important protocol deviations will be summarized and listed.

Protocol deviations will be tracked by the study team throughout the conduct of the study. These protocol deviations will be reviewed to identify those considered as important as follows:

- Data will be reviewed prior to freezing the database to ensure all important deviations are captured and categorised in the protocol deviations dataset.
- This dataset will be the basis for the summaries of important protocol deviations.

No per protocol analysis is planned for this study.

6.1.4. Prior and Concomitant Medications

Prior and concomitant medications will be coded using the newest versions of both the GSK Drug and the World Health Organization Drug Dictionary (WHODD). However, the summary will be based on GSK Drug dictionary only. The summary of concomitant medications will be provided by ingredient, i.e., multi-ingredient medications will be summarized for each individual ingredient rather than a combination of ingredients. The summary will be created using ingredient base names, i.e., ingredients with the same base name but different salt will appear under one base name in the summary. Anatomical Therapeutic Chemical (ATC) classifications will not appear in the summary, unless otherwise specified.

Concomitant medications will be summarized, where:

- A prior medication is defined as any medications that is started and ended prior to the date of single dose.
- Medications initiated after the single dose or initiated prior to the single dose and continued after the single dose will be counted as concomitant medications.

A medication that cannot be determined as prior or concomitant medication due to partially or completely missing start/stop date will be classified as the worst case, i.e., concomitant.

6.1.5. Study Intervention Compliance

Not Applicable.

6.2. Appendix 2 Data Derivations Rule

6.2.1. Study Period

Assessments and events will be classified according to the time of occurrence of relative dosing.

6.2.2. Study Day and Reference Dates

The safety reference date is the study intervention start date and will be used to calculate study day for safety measures.

The study day is calculated as below:

- Assessment Date = Missing → Study Day = Missing
- Assessment Date < Reference Date → Study Day = Assessment Date – Ref Date
- Assessment Date ≥ Reference Date → Study Day = Assessment Date – Ref Date + 1

6.2.3. Assessment Window

Assessment windows are described in Table 3 of the protocol.

6.2.4. Multiple measurements at One Analysis Time Point

Mean of the measurements (e.g., ECG) will be calculated and used in any derivation of summary statistics but if listed, all data will be presented.

If there are two values within a time window the value closest to the target time for that window will be used. If values are the same distance from the target, then the mean will be taken.

Participants having both High and Low values for Normal Ranges at any post-baseline visit (including post-baseline unscheduled assessments) for safety parameters will be counted in both the High and Low categories of “Any visit post-baseline” row of related summary tables.

6.2.5. Handling of Partial Dates

Element	Reporting Detail
General	
• Partial dates will be displayed as captured in participant listing displays.• However, where necessary, display macros may impute dates as temporary variables for sorting data in listings only. In addition, partial dates may be imputed for ‘slotting’ data to study phases or for specific analysis purposes as outlined below.

Element	Reporting Detail				
	
 • Imputed partial dates will not be used to derive study day, time to onset or duration (e.g., time to onset or duration of adverse events), or elapsed time variables (e.g., time since diagnosis). In addition, imputed dates are not used for deriving the last contact date in overall survival analysis dataset. 				
Adverse Events	
 • Partial dates for AE recorded in the CRF will be imputed using the following conventions: 
 
 Missing start day	 If study intervention start date is missing (i.e. participant did not start study intervention), then set start date = 1st of month. Else if study intervention start date is not missing: 
 • If month and year of start date = month and year of study intervention start date, then 
 – If stop date contains a full date and stop date is earlier than study intervention start date, then set start date= 1st of month. – Else set start date = study intervention start date. 	
 
 	Else set start date = 1st of month.	
 
 	Missing start day	If study intervention start date is missing (i.e. participant did not start study intervention), then set start date = 1st of month. Else if study intervention start date is not missing: 
 • If month and year of start date = month and year of study intervention start date, then 
 – If stop date contains a full date and stop date is earlier than study intervention start date, then set start date= 1st of month. – Else set start date = study intervention start date. 		Else set start date = 1st of month.
Missing start day	If study intervention start date is missing (i.e. participant did not start study intervention), then set start date = 1st of month. Else if study intervention start date is not missing: 
 • If month and year of start date = month and year of study intervention start date, then 
 – If stop date contains a full date and stop date is earlier than study intervention start date, then set start date= 1st of month. – Else set start date = study intervention start date. 				
	Else set start date = 1st of month.				
	
 
 Missing start day and month	 If study intervention start date is missing (i.e. participant did not start study intervention), then set start date = January 1. Else if study intervention start date is not missing: 
 • If year of start date = year of study intervention start date, then 
 – If stop date contains a full date and stop date is earlier than study intervention start date, then set start date = January 1. – Else set start date = study intervention start date. 	
 
 	Else set start date = January 1.	
 
	Missing start day and month	If study intervention start date is missing (i.e. participant did not start study intervention), then set start date = January 1. Else if study intervention start date is not missing: 
 • If year of start date = year of study intervention start date, then 
 – If stop date contains a full date and stop date is earlier than study intervention start date, then set start date = January 1. – Else set start date = study intervention start date. 		Else set start date = January 1.
Missing start day and month	If study intervention start date is missing (i.e. participant did not start study intervention), then set start date = January 1. Else if study intervention start date is not missing: 
 • If year of start date = year of study intervention start date, then 
 – If stop date contains a full date and stop date is earlier than study intervention start date, then set start date = January 1. – Else set start date = study intervention start date. 				
	Else set start date = January 1.				

Element	Reporting Detail					
	Missing end day	A '28/29/30/31' will be used for the day (dependent on the month and year).				
	Missing end day and month	No Imputation				
	Completely missing start/end date	No imputation				
Concomitant Medications/Medical History	
 Partial dates for any concomitant medications recorded in the CRF will be imputed using the following convention: 
 
 Missing start day	 
If study intervention start date is missing (i.e. participant did not start study intervention), then set start date = 1st of month.
 
Else if study intervention start date is not missing:
 
 If month and year of start date = month and year of study intervention start date, then 
 If stop date contains a full date and stop date is earlier than study intervention start date, then set start date= 1st of month. Else set start date = study intervention start date. 
Else set start date = 1st of month.
 	
 
 Missing start day and month	 
If study intervention start date is missing (i.e. participant did not start study intervention), then set start date = January 1.
 
Else if study intervention start date is not missing:
 
 If year of start date = year of study intervention start date, then 
 If stop date contains a full date and stop date is earlier than study intervention start date, then set start date = January 1. 	
 
		Missing start day	
If study intervention start date is missing (i.e. participant did not start study intervention), then set start date = 1st of month.
 
Else if study intervention start date is not missing:
 
 If month and year of start date = month and year of study intervention start date, then 
 If stop date contains a full date and stop date is earlier than study intervention start date, then set start date= 1st of month. Else set start date = study intervention start date. 
Else set start date = 1st of month.
	Missing start day and month	
If study intervention start date is missing (i.e. participant did not start study intervention), then set start date = January 1.
 
Else if study intervention start date is not missing:
 
 If year of start date = year of study intervention start date, then 
 If stop date contains a full date and stop date is earlier than study intervention start date, then set start date = January 1.
Missing start day	
If study intervention start date is missing (i.e. participant did not start study intervention), then set start date = 1st of month.
 
Else if study intervention start date is not missing:
 
 If month and year of start date = month and year of study intervention start date, then 
 If stop date contains a full date and stop date is earlier than study intervention start date, then set start date= 1st of month. Else set start date = study intervention start date. 
Else set start date = 1st of month.
					
Missing start day and month	
If study intervention start date is missing (i.e. participant did not start study intervention), then set start date = January 1.
 
Else if study intervention start date is not missing:
 
 If year of start date = year of study intervention start date, then 
 If stop date contains a full date and stop date is earlier than study intervention start date, then set start date = January 1. 					

Element	Reporting Detail
	
– Else set start date = study intervention start date. 
Else set start date = January 1.

Missing end day	A '28/29/30/31' will be used for the day (dependent on the month and year).
Missing end day and month	A '31' will be used for the day and 'Dec' will be used for the month.
Completely missing start/end date	No imputation
Age	
• Age will be calculated based on the Pre-Screening Visit date (or Screening if pre-screening not performed).

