### **8.1.2. Medical history**

The participant's medical history will be obtained by interviewing the participant and/or review of the participant's medical records. Any pre-existing conditions, signs and/or symptoms present prior to study start will be recorded in the eCRF.

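### The SAP's partial-date rule ignores a month-and-year stop date before dosing, so a year-only start is set to the dosing date, after the record's own imputed stop

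*SAP*

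**What the plan says.** SAP Section 6.2.5 has start-date rules for adverse events and, in a second row, for medications. They share the same structure.

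- **Day and month missing, year equal to the dosing year.** January 1 is used only under this condition: "If stop date contains a full date and stop date is earlier than study intervention start date, then set start date = January 1". In every other case: "Else set start date = study intervention start date".
- **Day missing, month and year equal to those of dosing.** The test is parallel: "If stop date contains a full date and stop date is earlier than study intervention start date, then set start date= 1st of month". The default is again the dosing date.
- **Stop date with the day missing.** "A '28/29/30/31' will be used for the day (dependent on the month and year"; that is, month-end. With day and month both missing, a medication stop becomes 31 December, and an AE stop is left unimputed.

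The general paragraph of 6.2.5 allows imputed dates to be used for slotting "data to study phases or for specific analysis purposes as outlined below". It bars them from study day, time to onset and duration, and says that listings show dates as captured.

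SAP Section 6.1.4 classifies medications: "A prior medication is defined as any medications that is started and ended prior to the date of single dose". Its worst-case rule (concomitant) is for medications whose status cannot be determined from the dates. SAP Section 4.5.1 calls an AE treatment emergent if its onset is on or after the treatment start date.

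The medication row is headed "Concomitant Medications/Medical History", but the sentence beneath introduces the convention for concomitant medications only.

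**The concern.** The stop-date test exists so that a record known to have finished before dosing is not given a start at dosing. It fails when the stop is known to the month but not the day, although a stop in any month before the dosing month is just as conclusive as a full date. The table then contradicts itself, because its own end-date rule puts the stop before the start it has just assigned.

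Two classifications are at stake. A finished medication can enter the concomitant-medication summary, and a finished pre-dose AE can enter the treatment-emergent tables. The AE rule is also at odds with Section 4.5.1. There, an AE with a completely missing start is assumed treatment emergent only if its end date is on or after treatment start. An AE with no start date and a stop in an earlier month is therefore not captured by that assumption, whereas the same AE with its start year recorded is classed as treatment emergent.

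**Working it through.** No sample size or error rate is involved. The check applies the rules of 6.2.5 literally to example records. The dosing date of 18 October 2023 is an assumption, used only to make the cases concrete.

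**Inputs (all SAP 6.2.5):** the full-stop-date test, the default to the dosing date, and the month-end and 31 December stop rules for medications.

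| Recorded start | Recorded stop | Start by rule | Stop by rule | Result |
|---|---|---|---|---|
| 2023 | Jun 2023 | 18 Oct 2023 | 30 Jun 2023 | starts after it stops |
| 2023 | 15 Jun 2023 | 1 Jan 2023 | 15 Jun 2023 | correct |
| 2023 | Oct 2023 | 18 Oct 2023 | 31 Oct 2023 | not reversed |
| 2023 | 2023 | 18 Oct 2023 | 31 Dec 2023 | not reversed |
| Oct 2023 | Oct 2023 | 18 Oct 2023 | 31 Oct 2023 | not reversed |
| Sep 2023 | Sep 2023 | 1 Sep 2023 | 30 Sep 2023 | unaffected |
| 2022 | Jun 2023 | 1 Jan 2022 | 30 Jun 2023 | unaffected |

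In the first case the gap is 31 (July) + 31 (August) + 30 (September) + 18 (October) = 110 days. The first two rows differ only in whether the stop day was recorded. Both medications had certainly ended before dosing.

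**How general this is.** Take a year-only start in the dosing year, dosing on the 15th of month m, and a month-and-year stop in months 1 to m.

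- Combinations: 1 + 2 + … + 12 = 12 × 13 / 2 = 78.
- Reversed: every combination with the stop month before the dosing month, 0 + 1 + … + 11 = 66.
- The other 12 have the stop in the dosing month. There the timing really is uncertain, and the default agrees with the worst-case rule of 6.1.4.
- Comparing the imputed stop with dosing first reduces the 66 reversals to 0.

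The 66 of 78 counts calendar combinations; it is not a rate of affected records.

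**Missing-day branch.** Here the start month is the dosing month. A partial stop in that month is imputed to month-end, which cannot precede dosing. Running every dosing date in 2023 gave 0 reversals.

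**Consequence for medications.** With a start of 18 October the record has not started before the dose, so it is not prior. With a stop of 30 June it neither began after the dose nor continued past it, so it also misses both descriptions of a concomitant medication. Only the worst-case class is left, although the recorded dates do settle the question.

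**Consequence for AEs.** The imputed onset equals the treatment start date, which satisfies Section 4.5.1.

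**The case against.** **Order of operations.** The SAP does not say whether stop dates are imputed before the start-date test. If they were, and an imputed stop counted as full, 30 June would precede dosing, the start would become 1 January and the reversal would vanish. Section 1 of the SAP also leaves further data-handling detail to the Output and Programming Specification, which is not among the documents. This is a possible reading. However, a test on whether the stop contains a full date most naturally refers to the date as recorded, and a programmer should not have to guess.

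**Classification is not dictated.** The example meets neither description of a concomitant medication, and 6.1.4 does not say that imputed starts override recorded dates. That is true, but the record also fails the prior definition, so the worst-case class is all that remains.

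**Reach.** This objection largely stands. Protocol Section 6.9 requires recording of medication taken at enrollment or during the study, and the screening schedule gives no look-back period for prior medication. It would therefore be wrong to treat every earlier month of the year as a realistic stop month. For AEs, collection starts at consent, and screening is at most 28 days before dosing. With dosing on 18 October that reaches back to 20 September, so only a September stop could qualify. Protocol Section 8.4.1 further limits pre-dose AEs to those related to study participation.

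**Medical history.** A reader might infer from the row label that every pre-existing condition with a partial start in the dosing month or year is made to begin at dosing. The protocol does describe history as prior ("Any pre-existing conditions, signs and/or symptoms present prior to study start will be recorded in the eCRF"). The documents do not carry the inference that far: the row's text names only concomitant medications, listings show dates as captured, and SAP Section 6.1.2 summarises conditions as of screening. What remains is an unclear scope.

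**Conclusion.** The point holds for one branch: day and month of the start missing, start year equal to the dosing year, and a month-and-year stop in a month before dosing. There the rule as written gives a start after the stop and removes a certainly prior medication from the prior class. It would also make a finished AE treatment emergent. This rests on reading the full-date test as applying to the recorded stop date.

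The size is small. The number of affected records cannot be derived from the documents, but it is likely to be low: mainly medication classification, and rarely AEs. Imputed dates do not feed study day, onset or duration, and the PK endpoints are untouched. Two wider conclusions are not supported: that all the start-date rows are faulty (the missing-day rows give no reversals), and that medical history is demonstrably misdated.

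**What to change.** In the rows for a start with day and month missing, for both AEs and concomitant medications, replace the stop-date condition with wording to this effect:

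> Where the start year is the dosing year, use January 1 if the stop date falls before dosing; for a partial stop date, apply this test to the latest date it could represent after end-date imputation. Otherwise use the dosing date.

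Leave the missing-day rows as they are.

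Separately, state whether the row labelled for medications and medical history applies to medical history. If it does, give history its own convention, so that a partial history start does not default to the dosing date.

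The cost is a short SAP wording change and a small edit to the date-imputation macro. No protocol amendment or extra data collection is needed.
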